**BP Measurement:**

We will use the initial BP measurement obtained once the patient has commenced HD (i.e. patient “hooked up” and blood present in both venous and arterial lines) for the *baseline BP*. Blood pressure will be measured as per routine procedures used in the participants’ HD units (usual arm/leg, usual BP cuff). Pre and post HD BP will be collected as per usual HD Unit practice. During HD, BP will be collected more frequently than the usual HD routine (q30 min) at q15min intervals or more frequently when clinically indicated based on patient symptoms or status. This timing will be pre-programmed into HD machines to minimize work for bedside HD nurses. However, bedside HD nurses will need to record each BP measurement on the HD run sheet. Research assistant and/or clinical exercise program kinesiologist will be present at each cycling session to ensure outcome data is being collected.

**Primary Outcome:** *Difference in rate of intradialytic hypotension* between the 2 study time periods (early and late intradialytic exercise). Rate of IDH will be reported as episodes of intradialytic hypotension per 100 hours of HD. Intradialytic hypotension will be defined as the composite of >20 mmHg drop from baseline BP OR a drop in systolic BP to <90 mmHg during HD. A >20 mmHg reduction in blood pressure is justified as this magnitude of reduction from baseline BP has been associated with occurrence of HD-induced cardiac injury. In addition, a nadir BP of <90mmHg is the only definition of IDH associated with increased risk of mortality.

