Intradialytic exercise has been shown to improve physical function and health-related quality of life and may ameliorate several dialysis-related symptoms. In addition, studies have demonstrated improved cardiac function, including increased left ventricular ejection fraction and decreased systolic pulmonary artery pressure and right ventricle size with intradialytic exercise. Initial concerns regarding the potential for intradialytic exercise to increase the rate of IDH have been mitigated by multiple interventional studies in which intradialytic exercise has been shown to be safe with minimal adverse effects. In addition, Leung et al demonstrated no increased IDH with intradialytic cycling when exercise was performed in the first half of HD as compared to no exercise. However, concerns regarding the potential of intradialytic exercise to increase frequency of IDH if exercise is performed in second half of HD remain. This is due to the potential risk of exacerbating intradialytic hypotension with post-exercise reductions in blood pressure in the latter half of dialysis when blood pressure (BP) and cardiac output may be lowest. This potential risk has not been rigorously studied prospectively and increased cardiac output and venous return associated with exercise may mitigate the effects of post-exercise hypotension in this setting. Farese et al. observed a significant (11 mmHg) increase in overall dialysis treatment systolic blood pressure with 3 weeks of passive cycling movement during HD (as compared to a non-intervention dialysis treatment), but the study did not comment on timing of intradialytic exercise. Rhee et al. found that decreases in systolic blood pressure improved as

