**Manitoba Renal Program's Clinical Intradialytic Cycling Program:**

In this pre-existing clinical program, individuals cycle on a stationary ergometer during their regular HD sessions while supervised by a kinesiologist. At present, 60 individuals are participating in this program at SCUDU and SOGH. Participants cycle in the first half of each HD session (usually 30-60 minutes) on TherapyCycle™ (Greely, CO) ergometers modified for dialysis chairs with a target exercise intensity of 3-4/10 on the Borg Rating of Perceived Exertion (RPE), which is considered to be moderate intensity. Rest periods are provided as needed if participants are unable to complete their target duration of continuous exercise. Duration of total exercise time and self-reported exercise intensity (Borg RPE) is recorded by participants/kinesiologist for each exercise session. The study kinesiologist adjusts cycling duration and ergometer resistance in consultation with each individual patient. HD unit staff assist with set up and monitoring of exercise sessions. In addition to routine HD monitoring (blood pressure and pulse before, after and every 30 min during HD and glucose pre and post HD in diabetics) participants have blood pressure, pulse and glucose (in individuals with diabetes) measured before and after completion of each intradialytic exercise session. The program is voluntary and participants choose not to cycle during some HD sessions. Program participants have physical function (4 metre gait speed, grip strength, shuttle walk test), health-related quality of life (EQ5D-3L) and self-reported physical activity level (Godin Leisure Time Exercise Questionnaire) measured prior to participating in the intradialytic program and every 6 months thereafter while enrolled in the exercise program.

Calgary and Edmonton have similar clinical intradialytic cycling programs from which

participants will be enrolled. Those 2 sites will receive ethics approval for their site through their respective University ethics boards.

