### **Data Collection and Management:**

Baseline demographic and clinical data will be collected from the hemodialysis chart. This will include age, sex, race, time on hemodialysis, hemodialysis access, dialysis vintage, comorbidities (including hypertension, diabetes, congestive heart failure and ischemic heart disease), amount of fluid removed at each HD, hemoglobin, Kt/V (dialysis efficacy), medications and blood work results as measured on last monthly bloodwork. Each patient will be assigned a unique study identifier. Routine hemodialysis run sheets on which all BP measurements during HD are recorded will be copied after each treatment (with all identifying information removed) and labeled with only the patients’ unique study identifier. The patient's identifying information with the coded study numbers will be stored in a hardcopy file in a locked filing cabinet. In addition, this information will also be stored in a password protected electronic file on a secure research server located at the University of Manitoba, Rady Faculty of Health Sciences, Max Rady College of Medicine that is accessible only to required study staff. Local research staff at each study site will enter de-identified study data from hard copy data collection sheets into a dataset that is housed on the secure research server. All electronic data files will be password protected. Datasets from Calgary and Edmonton will be password protected, combined together and analyzed in Winnipeg. Participant study questionnaires (completed as hard copies) will have no identifying information other than the unique study number. All hard copies will be stored in a locked filing cabinet in the primary investigator’s office at each site. Both electronic and hard copy data will be destroyed after a period of 10 years.

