**Sample Size Estimation:**

We consider a 20% increase in IDH rate with intradialytic exercise in the second half of HD to be clinically significant and unacceptable. A previous study of 42 HD patients who exercised in the first half of HD observed IDH rate was 130 episodes per 100 hours of HD.

Assuming a standard deviation of 50, a sample size of 75 individuals (approximately 2250 hours of HD) will give us 80% power to observe a 20% increase in IDH rate with one-sided alpha 0.05. To account for study dropout, we will recruit a total of 90 individuals in total at the 3 sites (30 from each site Winnipeg, Calgary, Edmonton).

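### The before- and after-cycling BP readings move with the assigned half of dialysis and can count as IDH, so the late period is expected to show somewhat more IDH even if timing has no effect

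*Protocol*

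**What the plan says.** - **Schedule.** Protocol, BP Measurement: readings are taken during HD every 15 minutes, "or more frequently when clinically indicated based on patient symptoms or status". The timing is programmed into the machines and is the same in both periods.
- **Extra readings.** Protocol, Manitoba Renal Program's Clinical Intradialytic Cycling Program: in addition to routine monitoring, BP is "measured before and after completion of each intradialytic exercise session". Calgary and Edmonton are described only as having similar programmes.
- **Data source.** Protocol, Data Collection and Management: "Routine hemodialysis run sheets on which all BP measurements during HD are recorded" are copied after each treatment. No type of reading is set aside.
- **Numerator.** Protocol, Primary Outcome: IDH is the "composite of >20 mmHg drop from baseline BP OR a drop in systolic BP to <90 mmHg during HD". There is no rule for when an episode begins, ends or is counted again.
- **Denominator.** Same section: "Rate of IDH will be reported as episodes of intradialytic hypotension per 100 hours of HD".
- **BP course.** Protocol, introduction: the concern about late exercise is the "latter half of dialysis when blood pressure (BP) and cardiac output may be lowest".
- **Model.** Protocol, Data analysis: the mixed model accounts for exercise duration, UF rate and within-patient data. Number of readings is not listed.
- **Planning values.** Protocol, Sample Size Estimation: in an earlier cohort exercising in the first half of HD, the "observed IDH rate was 130 episodes per 100 hours of HD". A 20% increase is treated as unacceptable.

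**The concern.** A rate per hour is comparable between periods only if BP is observed equally often, at equally risky times, in both. The 15-minute grid meets that condition. The before- and after-cycling readings do not: the assignment itself moves them from the half where BP is usually higher to the half where it may be lowest. Each gives an extra chance to register a qualifying drop, and that chance is larger in the late period. Dividing by hours does not correct for this. Nor does the crossover, because the difference belongs to the assigned timing and not to the patient.

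The bias runs in one direction, towards late exercise looking worse. That is the direction the one-sided sample-size calculation looks for, and it works against the no-difference result the protocol anticipates. Part of any observed late excess could come from where the cuff was inflated and not from exercise timing.

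**Working it through.** **Benchmarks from the protocol.** The planning rate is 130 per 100 h, or 1.3 per hour. The unacceptable increase is 0.20 × 130 = 26 per 100 h. At four grid readings per hour, 1.3/4 = 0.325, so 32.5% of grid readings would qualify if each were counted.

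**Assumptions (not in the protocol).** Session length L = 4 h, with 3.5 to 4.5 h as the range. Two extra readings per session, none coinciding with a grid reading. Every session cycled. Second-half readings r = 1.5 to 3 times as likely to qualify as first-half readings. No true timing effect.

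**Every qualifying reading counted.** With p = 0.325 the average of the two halves:

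- p1 = 2p/(1 + r) for the first half and p2 = r × p1 for the second
- early count per session = 1.3L + 2p1
- late count per session = 1.3L + 2p2

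| L (h) | r | Early | Late | Excess |
|---|---|---|---|---|
| 4 | 1.5 | 5.20 + 0.52 = 5.72 | 5.20 + 0.78 = 5.98 | 4.5% |
| 4 | 2 | 5.20 + 0.43 = 5.63 | 5.20 + 0.87 = 6.07 | 7.7% |
| 4 | 3 | 5.20 + 0.325 = 5.525 | 5.20 + 0.975 = 6.175 | 11.8% |
| 4.5 | 1.5 | 5.85 + 0.52 = 6.37 | 5.85 + 0.78 = 6.63 | 4.1% |
| 3.5 | 3 | 4.55 + 0.325 = 4.875 | 4.55 + 0.975 = 5.525 | 13.3% |

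At 4 h the differences are 100 × 2(p2 − p1)/4 = 6.5, 10.8 and 16.3 per 100 h for r = 1.5, 2 and 3, against 26.

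**Simulation under both counting rules.** There was no timing effect, with 40,000 sessions of 4 h per period and a 45-minute bout. SBP fell linearly by 10, 20 or 30 mmHg, with within-session SD 12 and 15-minute autocorrelation 0.3 or 0.7. The after-cycling reading was raised by 0 or 10 mmHg. All of these are assumed.

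- Every qualifying reading counted: late minus early was +3.9 to +19.8 per 100 h (4.4% to 11.1%).
- Only new entries into hypotension counted, so that consecutive low readings merge: +0.4 to +2.4 per 100 h (1.1% to 4.8%).
- 15-minute readings only: zero within simulation error under both rules (all within about 1.5 per 100 h).

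**Non-cycling sessions.** These have no before/after pair. Cycled sessions have 2/18 = 11% (4.5 h) to 2/14 = 14% (3.5 h) more readings, so the protocol's exercise versus non-exercise comparison is affected too.

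**The case against.** **Symptom-triggered readings.** A reader might infer that these also favour the early period. The documents do not support that. They are taken when clinically indicated, nothing ties them to the bout, and with no timing effect they fall equally in both periods. Staff presence at cycling sessions could raise detection, but the protocol does not say so.

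**Whether two extra readings exist at every site.** The pair is stated for Manitoba, on top of a 30-minute routine that the study replaces with 15 minutes. A before or after reading may coincide with a grid reading and add nothing. This stands as a limit on size. With one effective extra reading (L = 4, r = 2) the counts are 5.42 and 5.63, an excess of 4.0%. If only the 30 of 90 participants from Winnipeg had the pair, 10.8 per 100 h would become about 3.6.

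**Post-exercise rise.** The protocol cites a study in which SBP was raised immediately after exercise. A 10 mmHg rise lowered the per-reading excess in all six simulated settings (for example 10.6 to 9.3 per 100 h) without removing it. Under merging it raised the small excess (0.4 to 1.8 in the same setting), since one high reading can split a low run in two.

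**Episodes, not readings.** The outcome is worded as episodes, and merging leaves only about 1-5%. This stands. The 130 per 100 h rate looks high for merged episodes: at 30-minute readings, separate runs cannot exceed one per hour. But the protocol does not give the earlier study's reading interval or counting rule, so this is only suggestive.

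**A false-positive rate.** A reader might convert the excess into a chance of wrongly declaring late exercise harmful. That needs the SD of the within-patient difference, and the protocol does not say what its SD of 50 refers to. As a paired-difference SD it gives n = (50 × 2.486/26)² ≈ 23. With uncorrelated periods it gives (70.7 × 2.486/26)² ≈ 46. Neither is the stated 75, so no such rate should be quoted.

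**A matter for the SAP.** An unseen SAP may settle the counting rule. But the protocol itself fixes the schedule, data source, numerator and denominator, and following them as written produces the imbalance. Reading type is also best recorded when the data are collected.

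**Conclusion.** The point holds for the before- and after-cycling readings only. As written, the plan observes the second half of HD more often in the late period, and the primary rate does not correct for it. The expected effect is a modest spurious excess in the late period: roughly 4-13% per qualifying reading, or about 1-5% with merging, against the 20% called unacceptable.

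The direction rests on the protocol's own statement that BP may be lowest late in HD. The size rests on assumed session length, two non-coinciding extra readings in every session, and an assumed fall in BP. Overlap with the grid, or fewer sites taking the pair, would reduce it. It would be too strong to say that the trial will show late exercise to be harmful. The documents support an expected bias of uncertain size, worth removing because removal is cheap.

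**What to change.** 1. State in the primary outcome that before- and after-cycling readings do not count towards the primary IDH rate. The pre-programmed 15-minute readings and clinically indicated readings count, by the same rule in both periods and in non-cycling sessions. A reading that falls on the 15-minute schedule counts as scheduled even if it also serves as the before or after reading.
2. Flag reading type (scheduled, clinically indicated, before/after cycling) on the run sheet and at data entry, at all three sites.
3. Report two sensitivity analyses: all readings, and 15-minute readings only. The second also covers any difference in how often clinically indicated readings are taken.
4. Fix one episode-counting rule, consistent with the rule behind the 130 per 100 h planning rate.

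The cost is a sentence or two in the outcome definition and one data field. Clinical monitoring is unchanged. The small downside is that a dip seen only on a before- or after-cycling reading leaves the primary count, though it stays in the all-readings sensitivity analysis. Clinically indicated readings are kept in the primary count because dropping them could discard genuine hypotension that the symptomatic secondary outcome would not fully recover.

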**Secondary Outcomes:**

1. Difference in rate of intradialytic hypotension (episodes of hypotension per 100 hours of HD) between the 2 study time periods (early and late dialytic exercise) as defined by a >20 mmHg drop from baseline BP AND associated with symptoms (abdominal discomfort, yawning, sighing, nausea, vomiting, muscle cramps, restlessness, dizziness or fainting, and anxiety) or requiring intervention. Although this definition is proposed by KDOQI, practically it is harder to capture for research purposes. Nonetheless, we will capture as a secondary outcome to ensure no difference in rate between two groups.
2. Difference in frequency and severity of dialysis related symptoms during the weeks that incorporate intradialytic cycling in the first part of the HD sessions as compared with symptoms when intradialytic cycling is performed during the second half of HD will be measured using the symptom burden score as measured by the Dialysis Symptom Index (DSI). The DSI (Appendix 1) is a 30-item self-administered questionnaire with low administrative burden that measures the presence (yes/no) and severity (5 point Likert-scale) of common symptoms in HD patients (cramping, nausea, dizziness, fatigue, chest pain, and shortness of breath) and has been shown to be reliable and valid. Participants will complete the DSI at time of consent and then weekly at the end of the

midweek HD session (on Wed for MWF HD shifts and on Thurs for TTS HD shifts) for the duration of the study (i.e. each participant will complete the DSI a total of 5 times over the study).

3. Difference in time for recovery post-dialysis when exercise is performed during first half of dialysis as compared with time for recovery post-dialysis when exercise is performed during the latter half of HD: at each study assessment, participants will be asked to answer the question “Approximately how much time does it take to recover from a dialysis session”. Answers will be recorded in minutes. Prolonged post-HD recovery time, defined as the answer to the question “How long does it take to recover from a dialysis session” has been identified as a troubling symptom complex and important outcome unique to individuals receiving HD.

### **Data Collection and Management:**

Baseline demographic and clinical data will be collected from the hemodialysis chart. This will include age, sex, race, time on hemodialysis, hemodialysis access, dialysis vintage, comorbidities (including hypertension, diabetes, congestive heart failure and ischemic heart disease), amount of fluid removed at each HD, hemoglobin, Kt/V (dialysis efficacy), medications and blood work results as measured on last monthly bloodwork. Each patient will be assigned a unique study identifier. Routine hemodialysis run sheets on which all BP measurements during HD are recorded will be copied after each treatment (with all identifying information removed) and labeled with only the patients’ unique study identifier. The patient's identifying information with the coded study numbers will be stored in a hardcopy file in a locked filing cabinet. In addition, this information will also be stored in a password protected electronic file on a secure research server located at the University of Manitoba, Rady Faculty of Health Sciences, Max Rady College of Medicine that is accessible only to required study staff. Local research staff at each study site will enter de-identified study data from hard copy data collection sheets into a dataset that is housed on the secure research server. All electronic data files will be password protected. Datasets from Calgary and Edmonton will be password protected, combined together and analyzed in Winnipeg. Participant study questionnaires (completed as hard copies) will have no identifying information other than the unique study number. All hard copies will be stored in a locked filing cabinet in the primary investigator’s office at each site. Both electronic and hard copy data will be destroyed after a period of 10 years.

### **Data analysis:**

Demographic and baseline clinical data will be analyzed using the appropriate descriptive statistics and presented as mean (standard deviation), median (interquartile range), and proportion for parametric, non-parametric and categorical data, respectively. Linear mixed models will be used to analyze the associations between timing of exercise (first half or second half of HD) and intradialytic hypotension while accounting for duration of exercise, UF rate and

within patient data. Mean symptom burden score will be stratified by timing of intradialytic exercise and compared using paired Student's t-test. Similar analysis will be performed for time for recovery post HD.

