**Recruitment, Enrolment and Assessments:**

Individuals receiving HD at SCDU and SOGH who are currently participating in the Manitoba Renal Program's clinical intradialytic cycling program (see below) will be contacted by dialysis unit staff regarding their interest in being approached to participate in this study. If agreeable to initial approach, study staff will visit patients during their usual HD session, provide information about the study and obtain written consent. We plan to recruit a total of 30 patients from Winnipeg. These patients will act as their own comparisons. All recruited patients are already cycling during their regularly scheduled HD sessions as part of the MRP clinical intradialytic cycling program. No new intervention will be applied as part of this study. Participants will simply change the timing of their intradialytic cycling for 2 out of the 4 weeks of the study. Participants will be randomly assigned (computer generated randomization list generated by a third party) to study Group 1 or Group 2 with even distribution between each group. Similar recruitment procedures will occur in Calgary and Edmonton.

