**Intervention:**

To facilitate study implementation and optimize use of exercise resources and equipment, participants at each site will be randomly split into 2 groups. Group 1 will perform 2 weeks of their usual intradialytic cycling (6 sessions) during the first half of their usual HD and then perform 2 weeks of intradialytic cycling (6 sessions) during the second half of their usual HD. Group 2 will perform the intervention in reverse order to Group 1 (See Figure 1). No washout period is required as there is no biological plausibility for carry over effect. However, as participation in the cycling program is voluntary, some participants may choose not to exercise during some of their HD sessions. We will monitor these non-cycling sessions for IDH as well and will compare IDH rate in these non-exercise sessions with IDH rate during sessions when intradialytic exercise was performed.

Participants will perform their usual duration and intensity of intradialytic cycling at each HD session as per clinical intradialytic cycling protocol procedures (see below). Prescribed exercise time and intensity will remain unchanged over the course of the study.

We will attempt to keep dialysate composition, dialyzer, dialysate temperature, HD access, dialysis duration and medications unchanged over the course of the study, but will not intervene/interfere with usual clinical care. The research assistant will record any changes to dialysis prescription related to routine clinical care on a weekly basis.

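### The paired t-test fixed for symptom burden, and implied for recovery time, leaves out the period effect of the two-sequence crossover; the cost is some efficiency on secondary outcomes

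*Protocol*

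**What the plan says.** Protocol, Recruitment, Enrolment and Assessments: patients are randomised to Group 1 or Group 2 "with even distribution between each group".

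Protocol, Intervention: Group 1 cycles in the first half of dialysis for two weeks (6 sessions), then in the second half for two weeks. "Group 2 will perform the intervention in reverse order to Group 1". On the crossover itself the section says only this: "No washout period is required as there is no biological plausibility for carry over effect". That concerns carry-over. Neither this section nor any other deals with a change common to all patients between the two periods.

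Protocol, Data analysis: "Mean symptom burden score will be stratified by timing of intradialytic exercise and compared using paired" Student's t-test. For the other secondary outcome, "Similar analysis will be performed for time for recovery post HD". For IDH, a linear mixed model relates timing of exercise "and intradialytic hypotension while accounting for duration of exercise, UF rate and" within-patient data.

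Protocol, Secondary Outcomes: the Dialysis Symptom Index (DSI) is completed at consent and then weekly, so that "each participant will complete the DSI a total of 5 times over the study". This gives two scores in each two-week period.

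**The concern.** Because the two groups take the conditions in opposite order, period and timing are crossed and can be separated. That is what the second sequence buys. A paired t-test pools all late-minus-early differences as one sample and ignores which group they came from. If scores drift between the first and second two weeks, the drift adds to the differences in one group and subtracts from those in the other. The test then counts it as random variation between patients.

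Some drift is possible. The DSI is self-administered repeatedly, and the study "will not intervene/interfere with usual clinical care". At stake is the ability to detect a real early-late difference in symptoms or recovery time. Validity under balance is not at stake.

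The point does not depend on an unseen statistical analysis plan. Such a plan could add a term to a model, but it cannot add one to a t-test. It would have to replace the test that the protocol names.

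**Working it through.** **Inputs from the protocol.** Two sequences, allocated evenly. 90 recruited and 75 needed (Sample Size Estimation), so 15 losses are allowed for. The protocol states no power or alpha for symptoms or recovery time, so there is no figure of its own to reproduce here.

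**Assumptions.** Period shift *d* = 0.1, 0.26 or 0.52, in units of the SD of the within-patient difference; two-sided 5% test; the 15 losses fall at random. None of these is in the protocol.

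**Model.** The late-minus-early difference has mean τ + *d* in Group 1 and τ − *d* in Group 2, with SD 1 within each group.

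**1. Bias of the unadjusted mean.** Bias = *d*(n1 − n2)/N, which is zero when the sequences are equal.
- 40/35, *d* = 0.52: 0.52 × 5/75 = 0.035 SD
- 42/33, *d* = 0.52: 0.52 × 9/75 = 0.062 SD

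With 15 of 90 lost at random from 45/45, the chance of 40/35 or worse in a given direction is 12.9%, and of 42/33 or worse 1.1% (hypergeometric).

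**2. Variance that the paired test uses.** It is 1 + *d*²[1 − ((n1 − n2)/N)²], or 1 + *d*² at balance. At balance the point estimate is the same as the adjusted one, and only its standard error is overstated, by a factor √(1 + *d*²):
- *d* = 0.1: √1.0100 = 1.005
- *d* = 0.26: √1.0676 = 1.033
- *d* = 0.52: √1.2704 = 1.127

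**3. Operating characteristics.** Simulation with N = 75, averaged over the splits that random loss produces, 200,000 replicates. Power is for a true difference of 0.328 SD, which the adjusted analysis detects with 80%.

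| Shift *d* | CI width, paired vs adjusted | Type I error, paired | Type I error, adjusted | Power, paired | Power, adjusted |
|---|---|---|---|---|---|
| 0.1 | +0.4% | 4.9% | 5.0% | 80% | 80% |
| 0.26 | +3% | 4.5% | 5.0% | 78% | 80% |
| 0.52 | +13% | 3.1% | 5.1% | 72% | 80% |

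A repeat of the simulation agreed within simulation error. With the split held at 40/35, the paired test still stays below 5%: 4.5% at 0.26 SD and 3.5% at 0.52 SD.

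**4. Cost of including period.** SE factor = √[N(1/n1 + 1/n2)/4]:
- 38/37: 1.0001
- 40/35: √[75(1/40 + 1/35)/4] = 1.0022
- 42/33: √[75(1/42 + 1/33)/4] = 1.0073

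**5. IDH model, for comparison.** Take a random-intercept model on 6 + 6 sessions, with a session variance of 3 in the same units (assumed). Leaving period out multiplies the SE by √(1 + *d*²/11) = 1.0005, 1.003 and 1.012. One-sided type I error is 5.0%, 5.1% and 5.2%.

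**The case against.** The best defence is that the paired test is valid. Sequences are randomised evenly, the estimate is unbiased at balance, and the error rate is at or below nominal in every scenario with random loss. The protocol makes a power claim only for IDH, so no stated claim about symptoms or recovery time is broken. All of this stands, and it limits the point to efficiency.

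The size of any drift is also open to challenge. Patients have been on dialysis for more than three months and already cycle. The study lasts four weeks, prescribed exercise stays unchanged, and the team will try to hold the dialysis prescription and medications constant. The DSI is first completed at consent, so much of any first-administration effect falls before the comparison. Changes in individual care are not a common shift. This also stands: 0.52 SD is an extreme case, and at 0.1 SD the loss is trivial.

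Recovery time is tied less firmly to the t-test, since the protocol asks only for a similar analysis. The natural reading is still the same test.

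Two stronger readings are tempting, and the documents support neither.
- **The timing comparison is confounded with period, or false positives are inflated.** That needs completers who are clearly unequal by sequence as well as a real shift. At 45/30 the type I error would be 6.2% and 9.1% for shifts of 0.25 and 0.5 SD. Starting from 45/45, however, that split requires all 15 losses to come from one group.
- **The primary IDH analysis is wrong because its terms omit period.** The list of terms is brief and not stated to be complete, and a statistical analysis plan may add period. A model fitted to sessions is almost unaffected (SE at most +1.2%). Fitted to one rate per patient and period, it would behave much like the paired test, but the protocol does not say that it will be. Ultrafiltration rate and exercise duration vary by session, which points to the session level.

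**Conclusion.** The point holds as a low-priority improvement for two secondary outcomes. The protocol sets up a crossover that can remove a period effect, then names a test that cannot. If completers stay balanced, or are lost for reasons unrelated to sequence, the result is not materially biased. It is only less precise and more conservative than it need be, by +0.4%, +3% or +13% in interval width and by about 0, 2 or 8 points of power at the assumed shifts. If completers differ by sequence, the fraction (n1 − n2)/N of the shift also enters the estimate: 0.035 SD at 40/35 with the extreme shift. The shift sizes, the two-sided 5% level and random loss are assumptions.

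**What to change.** In Data analysis, replace the paired t-test for symptom burden, and the similar analysis for recovery time, with a period-adjusted crossover analysis. Fit a linear mixed model to each patient's two period means, with timing and period as fixed effects and a random patient effect. For complete pairs this is the same as comparing the within-patient differences (second period minus first) between Group 1 and Group 2 with a two-sample t-test and halving the estimate.

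The cost is one degree of freedom. The SE rises by 0% if balanced, 0.2% at 40/35 and 0.7% at 42/33. Outcomes, measurement scale and sample size do not change. Adding period to the IDH mixed model as well would keep the analyses consistent, if the statistical analysis plan does not already include it.
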